5.1.2 Randomized Treatment

During the induction phase:

Nivolumab (1 mg/kg) followed by ipilimumab (3 mg/kg) will be administered every 3 weeks, with 21 consecutive days defined as a treatment cycle. Troriluzole vs. placebo will be continuously self-administered orally twice a day (140 mg PO QAM and 280mg PO QPM**).

During the maintenance phase:

Nivolumab (480 mg IV) will be administered every 4 weeks, with 28 consecutive days defined as a treatment cycle. Troriluzole vs. placebo will be continuously self-administered orally twice a day (140 mg PO QAM and 280mg PO QPM**).

**This is the anticipated MTD from the Safety Run-In. If the Safety Run-In fallback cohorts are needed and the MTD is lowered, this will be amended.

Treatment will be administered on an outpatient basis. Reported adverse events and potential risks are described in Section 7. Appropriate dose modifications are described in Section 6. No investigational or commercial agents or therapies other than those described below may be administered with the intent to treat the participant's malignancy.

Table 5.13

Regimen Description – Induction					
Agent	Premedications; Precautions	Dose	Route	Schedule	Cycle Length
Troriluzole or placebo	Take with or without food.	1 cap oral Q AM; 2 caps oral QPM	Oral, 140 mg capsules	Days 1-21*	3 weeks
Nivolumab		1 mg/kg over 30 minutes**	IV	Day 1	

Ipilimumab		3 mg/kg over 30 minutes**	IV 0-60 min after completion of nivolumab through separate IV line	Day 1	

*The participant will be requested to maintain a medication diary of each dose of medication. The medication diary will be returned to clinic staff at the end of each cycle
 
** Infusion time windows of -5 min/+ 10 min are allowed
					

Regimen Description – Maintenance					
Agent	Premedications; Precautions	Dose	Route	Schedule	Cycle Length
Troriluzole or placebo	Take with or without food.	1 cap oral Q AM; 2 caps oral QPM	Oral, 140 mg capsules	Days 1-28*	4 weeks
Nivolumab		480 mg over 30 min**	IV	Day 1	

*The participant will be requested to maintain a medication diary of each dose of medication. The medication diary will be returned to clinic staff at the end of each cycle
 
** Infusion time windows of -5 min/+ 10 min are allowed
					

5.2 Pre-Treatment Criteria

Safety Run-In and Randomized Treatment:

Cycle 1, Day 1. The subject must meet all eligibility criteria on Day 1. Baseline laboratory and clinical evaluations are to be conducted within 1 week prior to start of protocol therapy. If the participant's condition is deteriorating, evaluations should be repeated within 48 hours prior to initiation of therapy. Complete blood count with differential and comprehensive metabolic panel results should be reviewed prior to treatment. It is recommended that participants receive all indicated routine immunizations prior to the start of treatment (due to possible effect on immunologic correlative science and desire to minimize toxicity during the induction phase).

Subsequent Cycles. Safety assessments, including complete blood count with differential and comprehensive metabolic panel results must be performed prior to administration of any study agent, excluding oral therapy, which is continuous. Study assessments and agents should be administered within + 7 days of the protocol-specified date for Days 1-309, and within + 14 days of the protocol-specified date for Days 337-673.

5.3 Agent Administration

Safety Run-In and Randomized Treatment:

Administration and Dosing. As nivolumab and ipilimumab are FDA approved for metastatic melanoma, administration will follow institutional standard/package insert. The IV agents are not vesicants or irritants. No observation period is necessary. Doses of nivolumab and ipilimumab are weight-based during the induction phase. It is acceptable to use baseline weight for all induction cycles. In the instance that the institutional policy is more strict, institutional policy should be followed. Refer to table in Section 5.1. Details are provided below for reference.

During the induction phase:

Nivolumab (1 mg/kg) followed by ipilimumab (3 mg/kg) 0-60 minutes later will be administered every 3 weeks, with 21 consecutive days defined as a treatment cycle. Troriluzole vs. placebo will be continuously self-administered orally twice a day (140 mg PO QAM and 280mg PO QPM; or twice daily per cohort assigned dose if in Safety Run-In). Due to toxicity, not all patients are expected to complete all 4 cycles of the induction. See section 6 for dosing modifications/omissions.

During the maintenance phase:

Nivolumab (480 mg IV) will be administered every 4 weeks, with 28 consecutive days defined as a treatment cycle. Troriluzole vs. placebo will be continuously self-administered orally twice a day (140 mg PO QAM and 280mg PO QPM; or twice daily per cohort assigned dose if in Safety Run-In).

Oral agents, troriluzole vs. placebo. Troriluzole or placebo in a blinded fashion will be self-administered orally with BID dosing Q 12 hours (\pm 2 hours). On a continuous basis throughout the protocol. Capsules can be taken with or without food; if a patient experiences nausea, taking the capsule with food is recommended. Capsules cannot be crushed, chewed, or dissolved. If a dose has been missed or it is vomited up, it should be skipped. Patients may choose to use an antiemetic prior to taking troriluzole if needed.

Order of administration: On Cycle 1 Day 1, the nivolumab will be administered first, followed by the ipilimumab, and in the evening, the first dose of troriluzole or placebo will be self-administered at home. For subsequent cycles, troriluzole or placebo will be self-administered in the morning before coming to the outpatient infusion center, followed by the infusion(s), and then troriluzole will be self-administered in the evening.

Management of infusion reactions: refer to institutional policy; see section 6.4 for additional guidance. Steroids should be avoided as a routine premedication due to possible interference with the efficacy of the study agents. Pre-medications are not required but are allowed for patients with previous infusion reaction.

Treatment Period.

The treatment period of the induction phase is Day 1-84 (12 weeks).

The treatment period of the maintenance phase is from Day 85 to 337 (36 weeks). Day

337 is the last protocol-directed infusion of nivolumab (see below) and the last dose of troriluzole.

Adherence/Compliance. At the visit, each subject will be given a bottle containing capsules of study drug. The participant will be requested to maintain a medication diary of each dose of medication. The medication diary will be returned to clinic staff at the end of each cycle. Unused study medication will be returned to the research pharmacy. At the end of each cycle of treatment, the actual amount of unused drug will be compared to the amount taken as recorded on the subject's medication diary. The desired level of compliance is >75%. If a subject is below that threshold, the treating investigator should assess barriers to compliance and address any correctable barriers (e.g. antiemetic therapy). Patients who cannot maintain this level of compliance may be removed from the study at the discretion of the treating investigator.

5.4 End of Treatment

Safety Run-In and Randomized Treatment:

The End of Treatment (EOT) visit, Day 337 (or sooner if the patient discontinues active treatment) is the last dose of nivolumab and the last dose of Troriluzole vs. placebo. EOT assessments are listed in Section 10 (Study Calendar).

Participants removed from active protocol therapy for unacceptable adverse event(s) will receive management and supportive care for the adverse event until resolution or stabilization of the adverse event, per the treating investigator. During this time, participants must present for in-person visits at least every 12 weeks \pm 1 week.

Following EOT, participants may continue on nivolumab therapy indefinitely, as it is FDA approved without a maximum duration. Continuation of nivolumab is not required for this protocol. Patients who have completed the last dose of study medication (Day 337) should discuss their individual treatment plans with their treating physician. See Section 5.9 for protocol-required follow up.

5.5 Concomitant Medication and Supportive Care Guidelines

Safety Run-In and Randomized Treatment:

Acceptable Concomitant Medications. All treatments that the investigator considers necessary for a subject's welfare may be administered at the discretion of the investigator in keeping with the community standards of medical care. All concomitant medication will be recorded on the case report form (CRF) including all prescription, over-the-counter (OTC), herbal supplements, and IV medications and fluids.

Selected acceptable medications include:

- Antiepileptic (anti-seizure, anticonvulsant) medications. *Exception:* Carbamazepine, which is a CYP1A2 inducer, is prohibited.

- Erythropoietin
- Hormone replacement therapy
- Immunizations. Routine vaccinations are permitted but discouraged during Days 1-84 when the most toxicity is expected. If the treating investigator feels that a vaccination is unsafe to delay (e.g. seasonal influenza immunization), the patient may receive the vaccination during Days 1-84. Vaccinations received during the study period should be documented as a concomitant medication.
- Anticoagulation. Prophylactic or treatment-dose anticoagulation is permitted when indicated. ASCO has recently published new a guideline on venous thromboembolism prophylaxis and treatment in patients with cancer. Intracranial or CNS bleeding within the past 4 weeks is considered a relative contraindication to therapeutic anticoagulation.³⁷
- Steroids (dexamethasone, prednisone, etc.) – allowable indications
 - During study participation, neurologic symptoms may arise or worsen. Steroids may be used to control neurologic symptoms. Steroid treatment ≤ 16 mg dexamethasone PO daily tapered in ≤ 4 weeks is allowed for the treatment of brain edema (single episode). If a second episode of brain edema requires steroid treatment, the Sponsor-Investigator must be consulted.
 - Systemic steroids may be used for treatment of irAEs.
 - A brief course (< 7 days) of corticosteroids for prophylaxis of side effects from SRT is permitted.
 - A brief course (< 7 days) of corticosteroids for prophylaxis (e.g., contrast dye allergy) or for treatment of non-autoimmune conditions (e.g., delayed-type hypersensitivity reaction caused by contact allergen) is permitted.
 - Intranasal, intra-articular, and inhaled steroids are acceptable for any indication.
 - NOTE: Patients who receive systemic corticosteroids for any reason (including toxicity or management of symptoms brain metastases) must be off corticosteroids or have tapered down to an equivalent dose of prednisone 10 mg/day (dexamethasone ≤ 1.5 mg PO daily) or less to continue immune checkpoint therapy.

Prohibited Medications

- Systemic steroids for indications other than the indications above
- No investigational or commercial agents or therapies other than those described below may be administered with the intent to treat the patient's malignancy.
- Prophylactic use of colony stimulating factors (CSFs) are not permitted. They may be needed for supportive care and should be discontinued when the event resolves/improves. If needed longer than 4 weeks, the subject must discontinue study treatment.
- IVIG

5.6 Concomitant Brain-Directed Stereotactic Radiation therapy during the study

Safety Run-In and Randomized Treatment:

Permitted Therapy: Brain-directed Stereotactic Radiotherapy (SRT), also called stereotactic radiosurgery (SRS). If a subject demonstrates clinical benefit, but disease progression in ≤ 4 intracranial metastases occurs, the investigators may prescribe SRT (single episode), and 2

scenarios are permitted as detailed below.

- If the patient is clinically stable, progression should be confirmed by follow-up imaging after 4 weeks. If progression is confirmed, the patient may undergo SRT treatment (single episode in 1 – 5* fractions) for ≤ 4 lesions and may receive ≤ 16 mg dexamethasone PO daily tapered in ≤ 4 weeks. Treatment with the study drugs can be resumed after taper completion as long as the patient does not demonstrate criteria for discontinuation.

Note: Treatment in 5 fractions is generally indicated for lesions in critical anatomical locations, such as in the brainstem or abutting the optic chiasm.

- If the patient is symptomatic as a result of the disease progression, and clinical assessment indicates a requirement for SRT without the delay imposed by the 4 week confirmatory scan, the patient may undergo SRT and may receive ≤ 16 mg dexamethasone PO daily tapered in ≤ 4 weeks. Treatment with the study drugs can be resumed after the completion of the taper as long as the patient does not demonstrate criteria for discontinuation.

As a general guide, efforts should be made to avoid radiotherapy within 2 weeks after a treatment of either nivolumab + ipilimumab combination therapy or nivolumab monotherapy and avoid treatment resumption until at least 1 treatment-cycle length after radiotherapy.

These guidelines are adapted from a previous protocol (Tawbi, *et al*) that allowed SRT for ≤ 3 lesions,³ and adapted as per Aoyama, *et al* to allow SRT to up to 4 lesions.⁶ The ability to use 5 fractions for lesions in anatomically critical areas as described above is a second adaptation.

Administration of SRT and size of irradiated target lesions will be recorded on case report forms. The data from subjects who receive on-study SRT will be analyzed as a “radiation salvage” subgroup.

Permitted Therapy: Palliative Radiotherapy to a non-target lesion. Radiation therapy may be performed to palliate an extracranial tumor as long as it is not a target lesion for tumor assessment.

5.7 Concomitant Surgery therapy during the study

Safety Run-In and Randomized Treatment:

If a subject has disease progression in the brain and craniotomy or other skull surgery is recommended per standard of care, a single surgical intervention is permitted with the approval of the Sponsor-Investigator. To remain on-study, the subject must have remaining measurable disease in the brain.

Surgery for non-cancer indications may be allowed. The case should be discussed with the Sponsor-Investigator.

5.8 Criteria for Taking a Participant Off Protocol Therapy

Safety Run-In and Randomized Treatment:

Duration of therapy will depend on individual response, evidence of disease progression and tolerance. In the absence of treatment delays due to adverse event(s), treatment may continue until Day 337 or until one of the following criteria applies:

- Disease progression, with the following exceptions:
 - To allow for the possibility of pseudoprogression, investigators may continue to treat a patient beyond progression until the next assessment if the investigator believes the patient is clinically benefitting (must document in progress note). If PD is confirmed on a subsequent scan, therapy must be discontinued.
 - Investigators may continue to treat a patient beyond progression if the progressing lesion(s) can be addressed with brain-directed SRT (See Section 5.6). *NOTE:* To continue on study after SRT, the subject must have at least 1 non-irradiated target lesion and/or non-target lesion in the brain or body.
- Intercurrent illness that prevents further administration of treatment
- Unacceptable adverse event(s)
- Participant demonstrates an inability or unwillingness to comply with the oral medication regimen and/or documentation requirements
- Participant decides to withdraw from the protocol therapy
- General or specific changes in the participant's condition render the participant unacceptable for further treatment in the judgment of the treating investigator

Participants will be removed from the protocol therapy when any of these criteria apply. The reason for removal from protocol therapy, and the date the participant was removed, must be documented in the case report form (CRF). Alternative care options will be discussed with the participant.

When a participant is removed from protocol therapy and/or is off of the study, the participant's status must be updated in OnCore in accordance with [REGIST-OP-1](#).

5.9 Duration of Follow Up

Safety Run-In and Randomized Treatment:

Participants will be followed with in-person visits on Days 421, 505, and 589, or until death, whichever occurs first. If they are receiving additional nivolumab, this should be documented in the progress notes and reported in the case report forms. Treatment-emergent AEs should continue to be monitored during the follow-up period (until resolution). New AEs during follow up that are not related to treatment should not be recorded.

Tumor assessments will be performed as per standard of care during Days 421-589 and will be captured on CRFs.

Day 673 is the last required in-person visit. Subjects will continue to be contacted (or their charts will be accessed) for information on subsequent therapy and vital status for a total of 3 years. The study team will contact participants by phone every 12 weeks (+/- 14 days) to assess survival.

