
g: Fresh biopsy of extracranial disease (optional). The second biopsy may occur at any time between Days 43 and 64 to facilitate scheduling. Patients will also have 2 CPT top tubes (10 mL tubes) drawn on the day of the fresh tumor biopsies. Biopsy and shipping must occur Monday – Thursday.
 
h: If patient is having a craniotomy per standard of care, tumor sample from brain metastasis and 1-2 green top vials of CSF will be collected when feasible.
 
i: Follow-up visits #2-4. If patients discontinue treatment early, they should be evaluated in-person every 84 days (or more frequently as indicated) until 5 Follow-Up visits have been completed.
 
j: Final In-Person visit. Survival data will continue to be collected for 3 years, unless patient dies or withdraws consent to be followed. The study team will contact participants by phone every 12 weeks (+/- 14 days) to assess survival.
													

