Following the Safety Run-in, all participants will be enrolled on the randomized portion of the study.

Primary Endpoint. The primary endpoint of the study is global progression-free survival in patients with melanoma brain metastases who are treated with INT vs. INP. Of particular interest will be PFS at 6 months.

PFS is defined as the time from random assignment to the earlier of death or documented disease progression in the intracranial or extracranial compartments. The follow-up of patients who have neither died nor progressed will be censored at the date of the last follow-up visit.

Secondary Endpoints. The secondary objectives and their associated endpoints evaluate other important clinical outcomes, including overall survival (OS), intracranial response rate (RR) and

PFS, extracranial RR and PFS, and safety (number of participants experiencing adverse events, particularly neurologic events). We will also investigate:

- tolerability (number of induction cycles administered, number of maintenance cycles administered)
- use of corticosteroids for management of symptomatic cerebral edema (number of participants)
- use of corticosteroids for management of immune related adverse events (number of participants who require prednisone ≥ 1 mg/kg or equivalent)
- frequency of clinically-indicated stereotactic radiation therapy to the brain on study (number of patients, number of instances and number of lesions irradiated)
- frequency of clinically-indicated surgical intervention to the brain on study (number of participants)

Planned subgroup analyses according to baseline characteristics:

- Prior anti-PD-1 exposure (yes vs. no – if yes then adjuvant vs. metastatic setting)
- Prior ipilimumab exposure (yes vs. no)
- Age (<65 years vs 65 years or older)
- ECOG (0 vs 1)
- LDH at baseline (normal vs. elevated)
- Number of brain metastases (<3 vs 3 or more)
- Brain-directed stereotactic radiation therapy prior to study entry (yes vs. no)
- Craniotomy prior to study entry (yes vs. no)

Planned subgroup analyses according to on-study events:

- On-study brain-directed stereotactic radiation therapy (yes vs. no)

Exploratory Endpoints:

- associations between BRAF/NRAS mutation status and response endpoints, as well as tissue biomarker profiles between paired tissues from extracranial and intracranial metastases from individual patients, where available

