13.2 Sample Size, Accrual Rate and Study Duration

Accrual Targets				
Ethnic Category	Sex/Gender			
	Females		Males	Total
Hispanic or Latino	1+		2=	3
Not Hispanic or Latino	39+		66=	105
Ethnic Category: Total of all subjects	40+		68=	108
Racial Category				

American Indian or Alaskan Native	0+	0=	0
Asian	1+	2=	3
Black or African American	0+	0=	0
Native Hawaiian or other Pacific Islander	0+	0=	0
White	39+	66=	105
Racial Category: Total of all subjects	40+	68=	108

Sample Size. The total sample size for this investigation is between 6 and 108 patients, which includes 6 - 18 patients in the safety run-in, and up to 90 patients in the randomized portion.

Sample size estimates for the randomized trial are based on a proportional hazards mixture cure model with type-I error of 0.1, uniform accrual over 24 months, and 12 additional months of follow-up. The six-month global PFS proportion in the INP arm is assumed to be 0.6³ and follows an exponential distribution; it is also assumed that approximately 30% of patients in the INP arm and 50% of patients in the INT arm are cured (odds ratio = 2.33). Under these assumptions, there would be 80% power to detect a 6-month PFS rate of approximately 0.8 in the INT arm (hazard ratio = 0.557).⁴²

Accrual rate. Assuming accrual of about 3 patients per month across 6 sites and an equal allocation between experimental and control arms, 36 patients will be accrued within one year.

Study duration. Assuming unequal protocol activation times and holding accrual for analysis of safety run-in, study duration will be 4-5 years.

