13.5 Analysis of Primary Endpoints

Primary Endpoint: The primary endpoint of the study is global progression-free survival in patients with melanoma brain metastases who are treated with troriluzole/ipilimumab/nivolumab (INT) vs. ipilimumab/nivolumab (INP).

Analysis of the primary endpoint will be based on the proportional hazards mixture cure model (PHMC) with treatment (INT/INP) as the only predictor. Modeling of parameter estimates of survival and cure will be semiparametric with bootstrapped standard errors and stratified by the randomization factors. Analyses will be conducted using the *smcure* package from R, the PSPMCM macro from SAS, or any modification to these packages available at the time of analysis. Inference will be based on Z-values and associated p-values. Cure proportions will be based on estimation from the incidence portion of the model and metrics of PFS from patients who are not cured will be based on the latency portion of the model. Comparisons of cure rates will be expressed as odds ratios with confidence intervals, and comparisons of PFS will be expressed as hazard ratios with confidence intervals. The distributions of events for INT and INP will be summarized using marginal survival function curves. Point estimates at 6 months will be presented with confidence intervals.

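### No progression data are requested after Day 589, although the primary PFS cure model assumes 12 to 36 months of follow-up, and this tilts the cure odds ratio towards troriluzole

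*Combined protocol and SAP*

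**What the plan says.** Section 5.9 and Study Calendar footnote e put standard-of-care tumor assessments on the CRF for Days 421 to 589. The Day 673 column of the calendar has an examination and laboratory tests but no MRI or CT mark. After that, Section 5.9 seeks contact or chart access "for information on subsequent therapy and vital status for a total of 3 years". Footnote j mentions survival only: "The study team will contact participants by phone every 12 weeks (+/- 14 days) to assess survival".

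The primary endpoint needs more than vital status. In Section 13.1, "PFS is defined as the time from random assignment to the earlier of death or documented disease progression", in either compartment. Section 13.2 sizes the trial on "uniform accrual over 24 months, and 12 additional months of follow-up", which is 12 to 36 months per patient. Section 13.5 fits a proportional hazards mixture cure model and states: "Cure proportions will be based on estimation from the incidence portion of the model". Patients without an event are censored at the last follow-up visit under Section 13.1, but at the last disease evaluation under Section 11.5.

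**The concern.** A mixture cure model separates patients who never progress from those who progress later. The information for that separation lies in the tail of the curve. From Day 589 one component of PFS (death) is still collected and the other (progression) is not requested.

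The gap is not neutral between arms. If troriluzole slows progression among uncured patients, more INT than INP patients are still waiting to progress at Day 589. When capture stops there, part of that delay is read as cure. Whether the drug cures more patients or only postpones progression is what the two-part model is meant to tell apart.

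**Working it through.** **Inputs.** From Section 13.2: INP six-month PFS 0.6, exponential latency; cured fraction 0.30 INP and 0.50 INT (odds ratio 2.33); latency hazard ratio 0.557; "type-I error of 0.1", sidedness not stated; 80% power; up to 90 randomized. Equal allocation gives 45 per arm. From Section 5.9: Day 589 / 30.4375 = 19.35 months.

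**The plan's own figure.** INP latency hazard: 0.3 + 0.7·exp(−6λ) = 0.6, so λ = 0.1412 per month. A log-rank-type sample size formula for this model, with two-sided 0.1 and INT six-month PFS of exactly 0.80 (hazard ratio 0.603), gives N = 89 and 80.5% power at 90, so the size reproduces. With the printed 0.557, INT six-month PFS is 0.5 + 0.5·exp(−6 × 0.0787) = 0.812, N is 80, and power at 90 is 84%. I use the printed 0.557 below.

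**Potential follow-up past Day 589.** (36 − 19.35)/24 = 69% of patients, counting those who have already had an event.

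**Uncured and progression-free at Day 589.**
- INP: 0.7·exp(−0.1412 × 19.35) = 0.046; the PFS curve stands at 0.346, plateau 0.30.
- INT: 0.5·exp(−0.0787 × 19.35) = 0.109; the curve stands at 0.609, plateau 0.50.

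**Expected events per arm.** With follow-up uniform on 12 to 36 months and cure fraction π:
45(1 − π){1 − [exp(−12λ) − exp(−36λ)]/(24λ)}
- INP: 31.5 × (1 − 0.0524) = 29.9.
- INT: 22.5 × (1 − 0.1749) = 18.6.
- Total: 48.4.

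The part after Day 589 (c = 19.35) is:
45(1 − π){0.694·exp(−λc) − [exp(−λc) − exp(−36λ)]/(24λ)}
- INP: 31.5 × (0.0451 − 0.0174) = 0.87.
- INT: 22.5 × (0.1514 − 0.0844) = 1.51.
- Total: 2.4 of 48.4, or 5%.

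**Effect on the model.** Semiparametric mixture cure fits with the zero-tail constraint, in large simulated samples, ignoring late deaths:

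| Scenario | Capture | Cure INP / INT | Cure odds ratio | Latency hazard ratio |
|---|---|---|---|---|
| Design | truth | 0.30 / 0.50 | 2.33 | 0.557 |
| Design | full | 0.31 / 0.53 | 2.55 | 0.61 |
| Design | to Day 589 | 0.34 / 0.60 | 2.9 | 0.74 |
| Pure delay | truth | 0.30 / 0.30 | 1.0 | 0.557 |
| Pure delay | full | 0.30 / 0.33 | 1.1 | 0.60 |
| Pure delay | to Day 589 | 0.35 / 0.45 | 1.6 | 0.74 |

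Repeat runs of the design scenario gave odds ratios of 2.5 to 2.55 (full) and 2.9 to 3.0 (to Day 589).

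**Late deaths.** These need an assumption that the documents do not give: median 6 or 12 months from progression to death. If later deaths count and survivors stay at risk, the cure odds ratio is 2.6 to 2.7. If survivors are instead censored at their last disease evaluation, and none is recorded after Day 589, the tail holds only deaths. The cure fractions then collapse towards zero in large samples and are unstable at N = 90 (SD of the log odds ratio about 6).

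**What does not move.** Simulated two-sided log-rank power at N = 90 is 0.84 with full capture and 0.85 with capture to Day 589. Six-month PFS lies well before the gap.

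**The case against.** The strongest reply is that little is lost. Only 5% of expected events fall in the gap, and the six-month estimate, which the plan singles out, is untouched. The shift in the log cure odds ratio, ln(2.9/2.55) = 0.13, is small against its sampling SD at N = 90 (0.46 or more in the simulations). All of this stands, and it limits the weight of the point. It does not remove a bias that runs in one direction in the quantities Section 13.5 uses for primary inference.

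Some stronger readings are tempting but not supported:
- A reader might infer that the design needs 36 months from everyone. The range is 12 to 36, and only the earliest enrollees reach the upper end. Even full capture gives 2.55 rather than 2.33, so part of the tail bias comes from limited follow-up.
- A reader might infer that late failures vanish. Deaths still count, and subsequent therapy with chart access would point to many progressions. What is missing is a requested progression date.
- A reader might infer that all time to the data cut is wrongly credited as progression-free under Section 13.1. If the last follow-up visit means Day 673, only 84 days are, covering about 0.4 (INP) and 0.6 (INT) progressions per 45, or 0.9 under a pure delay.
- A reader might infer that one late death would often take a PFS curve to zero. One simulation put at least one such death in 42% of INP arms, but it assumed 12 months' mean survival after progression and 0.3% monthly background mortality. It also requires the Section 11.5 rule with no later evaluation. That describes the conflict between 11.5 and 13.1 more than the Day 589 gap.

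Two passages might seem to fill the gap. The calendar's instruction to enter extra measurements concerns treatment cycles, which end at end of treatment. Section 11.3's call to document progression after stopping treatment concerns symptomatic deterioration.

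**Conclusion.** The point holds as a moderate, cheaply corrected weakness. The plan requests no progression data after Day 589, while its primary model assumes follow-up of up to 36 months and reads cure from the tail. About 2.4 of 48 expected events would not be recorded as progressions, more of them in INT. Without late deaths, the cure odds ratio moves from about 2.55 to about 2.9 and the latency hazard ratio from about 0.61 to 0.74. Under a pure delay, an odds ratio of 1.0 would be estimated at about 1.6.

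These figures rest on the Section 13.2 assumptions with the printed hazard ratio of 0.557, complete detection of progression up to Day 589, and no late deaths. The true INP tail may be flatter: Section 2.5 reports a fall of only 5% between 6 and 12 months in the reference study, against 60% to 43% under the design's exponential. Late INP progressions would then be fewer. The documents do not support a claim that the six-month comparison or the trial's power is compromised.

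**What to change.** 1. In Section 5.9, footnote j and the CRF, at the Day 673 visit and at each existing 12-weekly contact or chart review up to the PFS data cut, record until first progression: the date, site and basis of first progression, and the date of last brain and body imaging.
2. In Sections 11.5 and 13.1, state one PFS censoring rule for living patients: the date of last disease evaluation, now including these later evaluations. The two changes belong together, because without the later evaluations this rule leaves a tail made up only of deaths.
3. Keep death from any cause as a PFS event in the primary analysis. Censoring deaths that follow a long gap in imaging may be a sensitivity analysis only. As a primary rule it would treat probable unrecorded progressions as non-events and could itself inflate cure.

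The cost is a few CRF fields at contacts that already take place and a sentence in each of two sections, with no extra visits or scans. The downside is that late progressions come from routine-care scans and are less precisely dated. Some tail bias remains, because follow-up is limited and some patients may have no late scan.
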